Lifestyle interventions have had established efficacy for over a decade but are still not widely disseminated, largely due to high cost and patient and provider burden.¹ Online social networks are an alternative way to deliver lifestyle counseling and delivery via this modality may virtually eliminate patient visits, the main source of cost and burden of traditional modalities. Interactions in online social networks are frequent, brief, and asynchronous because users login to their online communities during downtime during work and leisure time, or when they simply feel a need for social connection. As such, social media becomes embedded into people's daily lives. By using them we have a means to embed health behavior change agents into people's daily lives. Thus far in the

¹The term "prospectively assigned" refers to a pre-defined process (e.g., randomization) specified in an approved protocol that stipulates the assignment of research subjects (individually or in clusters) to one or more arms (e.g., intervention, placebo, or other control) of a clinical trial. ²An intervention is defined as a manipulation of the subject or subject's environment for the purpose of modifying one or more health-related biomedical or behavioral processes and/or endpoints. Examples include: drugs/small molecules/compounds; biologics; devices; procedures (e.g., surgical techniques); delivery systems (e.g., telemedicine, face-to-face interviews); strategies to change health-related behavior (e.g., diet, cognitive/behavioral therapy, exercise, development of new habits); treatment strategies; prevention strategies; and, diagnostic strategies. ³ 3.Health-related biomedical or behavioral outcome is defined as the pre-specified goal(s) or condition(s) that reflect the effect of one or more interventions on human subjects' biomedical or behavioral status or quality of life. Examples include: positive or negative changes to physiological or biological parameters (e.g., improvement of lung capacity, gene expression); positive or negative changes to psychological or neurodevelopmental parameters (e.g., mood management intervention for smokers; reading comprehension and /or information retention, behavioral intervention for psychiatric symptoms); positive or negative changes to disease processes; positive or negative changes to health-related behaviors; and, positive or negative changes to quality of life.

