Our pilot work reveals important potential advantages of social network delivered programs over traditionally delivered programs. First, online social networks overcome patient barriers such as scheduling, transportation, weather, and childcare. Second, this modality overcomes implementation barriers by not requiring space for visits, not limiting patient census due to daytime work schedules (e.g., traditional groups typically must be scheduled on weekday evenings or early mornings which limits the number of time slots available to treat patients in a week), and by more efficiently using counselor time (e.g., time commitment of 13 minutes per day for 12-15 patients). Third, online social networks are highly conducive to more immediate feedback. Counselors log in briefly twice daily which gives participants frequent opportunities for contact during the week. In focus groups, participants expressed that they liked daily albeit brief access to a counselor since they could get assistance on days they were struggling, rather than wait for weekly group meetings. Behavioral theory has long shown that the longer feedback is delayed, the less impact it has on behavior. Fourth, this modality may be more conducive to participants building a sustainable social network to support their weight loss journey after the intervention ends. Participants continue to be linked with each other on the social network after the study. Also, we will share content with them from online resources (e.g., weight loss blogs both peer and professional), which connects them to the informal weight loss community on Twitter. Finally, we will explore proposed predictors to determine for whom the online modality is best suited. Findings from this study may support an intervention delivery modality that is more conducive to settings like worksites, health plans, and clinics that serve large populations but have limited space, staffing, and resources for traditional in person interventions. If this efficacy trial is successful, we plan an effectiveness trial in a worksite setting to build upon our previous worksite interventions.⁴

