- Traditional participants will receive the DPP intervention during in-person group visits. Groups will include 18 participants each. During the first 6 months, groups will be held weekly for 8 weeks, then biweekly for 16 weeks. Groups will be held monthly between 6- and 12-months. There will be a total of 22 groups and each group will last 90 minutes (except for the first group which will be extended to 2 hours to accommodate the orientation) and each one will be audio recorded to track intervention-adherence. Participants will have weight taken in-person before the start of each group. During the weeks participants do not have a group, they will be encouraged to take their weight at home and e-mail it to study staff. Staff will e-mail them during these weeks asking for their current weight. The e-mail text wording is included in the measures attachment.
- Get Social participants will receive the DPP intervention in a "protected" Twitter group. Where participants and counselors will activate the "protected tweets" privacy setting so that the tweets are only viewable to each other. The DPP content has been restructured to deliver in an online context. The delivery includes a morning and evening post each day. The online coaches will log in twice daily to respond to questions, address concerns, and encourage engagement. Participants will receive an e-mail asking for their current weight, the minutes per week they used Twitter, and questions about treatment receipt. These e-mails will be sent during the same weeks that the Traditional participants have a group. The questions for this survey will all appear together accessible by one link. See measures attachment for survey. When reporting time on Twitter, participants will Androids will be asked to download an app called App Usage Tracker. This app is free and downloaded from the Play Store and tracks time spent on apps.
- Interventionists will be asked at to complete a survey at the 6 month timepoint. The survey link will be emailed at the 6 month time point in each wave. The survey will ask about their experience delivering the intervention. If they do not respond we will follow up with them via email or phone. Once they have delivered interventions to participants in both the Get Social and Traditional conditions the survey will also ask for their opinions comparing and contrasting their preferences for each condition.

Follow up:

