Linear multivariable models will be used to estimate change in daily caloric intake at 12 months; such models are reasonable given the target sample size and that changes in these outcomes are approximately normally distributed. We will examine the proportion of participants engaging in 150+ minutes/week of moderate/vigorous intensity physical activity (MVPA) using generalized estimating equations with a logit link function and incorporating repeated measures over time. For participants missing MVPA at either follow-up timepoint will use a baseline observation carried forward approach to impute their activity level (150+ vs <150 MVPA mins/week) at that timepoint. The distribution of secondary outcomes will be explored graphically and inform the primary outcome analysis; analyses will be modified as needed through transformation of the data.

Cost

We will calculate total intervention delivery costs per participant by treatment condition using time reported by intervention staff and convert to per-participant costs using national salary data from the Bureau of Labor Statistics. We will conduct sensitivity analyses to estimate a range of per-participant costs after varying the inputs (e.g., time spent conducting intervention, different intervention tasks, salary estimates). While we had originally aimed to examine costs for participants to participate in their respective intervention, we discovered methodologic challenges with collecting accurate and complete data from participants. As a result of what we learned, we have launched a separate study to develop methods for accurately collect participant time spent to participate in a social media delivered behavioral intervention. Without participant-level data, we are unable to conduct the analyses originally planned. Instead, we report the total intervention delivery costs per participant in both hours and dollars per participant for each of the two interventions.

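### The SAP calls a staff-labour figure the total delivery cost, so room use, which is greater in the Traditional arm, and other non-labour items are priced at zero

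*SAP*

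**What the plan says.** Aim 2 of the protocol asks whether online delivery costs less per participant than in-person delivery, and hypothesizes that it does. The protocol's Cost analysis section planned to compare total intervention costs and to look separately at administrative, interventionist and participant costs.

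The SAP's Cost section replaces this. The resource input is staff time: "We will calculate total intervention delivery costs per participant by treatment condition using time reported by intervention staff". The unit price is a salary; the SAP will "convert to per-participant costs using national salary data from the Bureau of Labor Statistics". Sensitivity analyses proceed by "varying the inputs (e.g., time spent conducting intervention, different intervention tasks, salary estimates"). The section ends: "we report the total intervention delivery costs per participant in both hours and dollars per participant for each of the two interventions". No room, facility, platform or other non-labour item is named. The reason given for narrowing the analysis is that accurate and complete participant data could not be collected.

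The protocol's background argues for the online programme partly on visits and space. It says online delivery "may virtually eliminate patient visits, the main source of cost and burden of traditional modalities", and that "this modality overcomes implementation barriers by not requiring space for visits". For the Traditional arm, the Intervention Phase section states "There will be a total of 22 groups and each group will last 90 minutes", with the first extended to two hours and 18 participants per group. The Orientation-Visits section requires each Get Social participant to attend a one-hour individual visit and a two-hour group visit, both in person. It also mentions a study website used only by Get Social participants.

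**The concern.** A figure presented as the total cost of delivering each programme should either include the premises and platform or say that it does not. Here both are set to zero by construction. The two zeros do not cancel, because the arms use rooms to different degrees and in-person attendance is the main thing that distinguishes them.

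The SAP's reason for dropping participant costs does not reach this item. Room-hours follow from the fixed session and orientation schedule and need no participant-level data.

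At stake is what Aim 2 can conclude. A labour-only contrast reported as a total would give the wrong size for any saving. If it showed no saving, a reader could not tell whether that reflected the programmes or the costing boundary.

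**Working it through.** **1. Session count.** From the Intervention Phase section: 8 weekly sessions, then biweekly for 16 weeks (16/2 = 8), then monthly for 6 months (6). 8 + 8 + 6 = 22. 22 x 90 min = 1,980 min = 33 h. This reproduces the 22 sessions and the 1,980 minutes in the Time Commitment table.

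**2. Traditional room-hours.** 22 x 1.5 h + 0.5 h (longer first session) = 33.5 h per group. 33.5/18 = 1.86 h per participant.

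**3. Get Social room-hours**, taking the protocol's goal of about 18 per condition per wave.
- Group orientation only: 2/18 = 0.11 h per participant.
- With the individual visit charged at the same rate: (2 + 18 x 1)/18 = 1.11 h per participant.

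**4. Net omission**, Traditional minus Get Social.
- Individual visit charged: (33.5 - 20)/18 = 0.75 h.
- Individual visit not charged: (33.5 - 2)/18 = 1.75 h.

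**5. In dollars.** The documents give no room rate, so $25-75 per hour is an assumption.

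| Assumed rate | Net, individual visit charged (0.75 h) | Net, visit not charged (1.75 h) |
|---|---|---|
| $25/h | $18.75 | $43.75 |
| $75/h | $56.25 | $131.25 |

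The first dollar column is the more even-handed, since an individual in-person visit may need a cheaper room but not a free one. Website hosting for Get Social would reduce either column by an amount that the documents do not give.

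**6. Could the direction of the cost comparison change?** This needs labour figures that the documents give only in part. The background cites 13 minutes of counselor time per day for 12-15 patients. Assume that this holds for 365 days and serves a group of 18, and assume a wage of $30 per hour.
- Get Social coach time: 13 x 365/60 = 79.1 h per group. Traditional leader contact: 33.5 h per group.
- Labour gap: (79.1 - 33.5) x $30 = about $1,367 per group, with Get Social dearer.
- Net room cost, individual visit charged: 13.5 h x $25-75 = $338-1,013 per group. This is below $1,367, so there is no reversal.
- Individual visit not charged: 31.5 room-hours per group. Break-even is 1,367/31.5 = about $43 per room-hour, inside the assumed range.
- Adding 20 h of Get Social orientation staff time (one staff member per visit) raises that break-even to (1,367 + 600)/31.5 = about $62.

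Coach time may fall over the year, and Traditional preparation, weigh-ins, off-week e-mails and make-up sessions are not counted. Either would narrow the labour gap. The sign therefore depends on inputs that the documents do not supply.

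**The case against.** The strongest reply is that this is a legitimate costing perspective, openly disclosed. The SAP states its formula beside the label. The protocol's section on interventionist data collection already says that timesheet hours feed the Aim 2 time and cost figures. The sensitivity inputs are introduced as examples, so a room rate is not barred. Hours are reported as well as dollars, and the session schedule is public, so a reader could add a local room rate. The reporting is descriptive, and the room omission runs against the trial's own hypothesis.

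Much of this stands, and it keeps the point small. It does not justify the word total, and it does not explain why an item that the schedule makes easy to compute is left out.

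Three stronger readings are tempting and are not supported.

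- A reader might infer that the protocol defined space as a cost that Aim 2 had to count. The background presents space as an implementation barrier, and names visits, not rooms, as the main source of cost. Premises are never listed as an Aim 2 component. They might fall under administrative costs, but that term is not defined.
- A reader might infer that the omission falls almost wholly on the Traditional arm. With the individual orientation charged, Get Social carries 1.11 of 2.97 unpriced room-hours (1.11 + 1.86), or 37%.
- A reader might infer that the omission reverses the comparison. Under the inputs tried above, reversal within the assumed rate range appears only when the individual orientation is charged nothing.

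**Conclusion.** The point holds as a minor one. Followed as written, the SAP reports staff labour under the name of a total and leaves a net 0.75 to 1.75 room-hours per participant unpriced. The hours rest on the documented schedule and 18 participants per group in each arm. The dollar range rests on a room rate that the documents do not give, and the unpriced website works the other way by an unknown amount.

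On room use, a finding that Get Social is cheaper would survive, though its size would be misstated. A finding of no saving would be unsafe. A change of direction is possible under some assumptions but is not shown. The primary outcome is unaffected, and no planned hypothesis test on cost remains for this to distort.

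**What to change.** In the SAP's Cost section:

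- Rename the labour-only result as staff labour cost per participant.
- Beside it, as a sensitivity analysis, report labour plus non-labour cost per participant. Take room-hours in both arms from the session and orientation schedule, including the Get Social individual orientations, and multiply by a stated low and high room rate. Add website hosting for Get Social.
- List the room rate and hosting cost among the inputs that are varied.

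If the second figure is not wanted, keep only the renamed one and limit the Aim 2 conclusion to staff labour cost.

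The cost is a few lines of SAP text and arithmetic from the existing schedule, with no new participant data. The downside is that one or two unit prices must be assumed, stated and varied.
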